#### 7.1.4 Body Surface Area

The overall Body Surface Area (BSA) affected by AD will be evaluated (from 0% to 100%) at the visits specified in [Table 1](#) before the study product administration. One subject's palm represents

[figure not shown]
1% of his or her total BSA. For all study visits except at screening, the BSA of involved skin will be measured with the SCORAD measurement (Section 7.1.3) and evaluated as a separate endpoint. To be eligible, subjects must have a BSA of  $\geq 10\%$  at Day 1.

### 7.1.5 Pruritus Numeric Rating Scale

The intensity of pruritus will be recorded for the entire duration of the treatment (daily) as specified in [Table 1](#) using a numeric rating scale (NRS) (21). This will be evaluated by asking subjects to assign a numerical score representing the worst intensity over the last 24 hours of their symptoms on a scale from 0 to 10, with 0 indicating no symptoms and 10 indicating the worst imaginable symptoms. The pruritus NRS is presented in [Figure 2](#).

Subjects will record the pruritus NRS in a diary before the study product administration. Subject compliance on the pruritus NRS will be followed at each clinic visit.

**Figure 2: Pruritus Numeric Rating Scale**

### 7.1.6 5D-Pruritus Scale

The 5-D Pruritus Scale will be evaluated at the visits specified in [Table 1](#). The 5-D Pruritus Scale is a 1-page, 5-question, validated questionnaire used in clinical trials to assess 5 dimensions of background itch: degree, duration, direction, disability, and distribution (22). Each question corresponds to 1 of the 5 dimensions of itch; subjects will rate their symptoms over the preceding 2-week period as “present” or on a 1 to 5 scale, with 5 being the most affected.

The 5-D Pruritus Scale is provided in [Appendix E](#).

## 7.2 Quality-of-Life Assessments

### 7.2.1 Patient-Oriented Eczema Measure

The Patient-Oriented Eczema Measure (POEM) will be assessed at the visits specified in [Table 1](#). The POEM developed by Charman et.al. (23, 24) is a self-assessment of disease severity by the subject. The POEM has a maximum value of 28 based on the subject’s response to seven questions scored from 0 to 4. A detailed description of the POEM assessment is provided in [Appendix F](#).

## 7.2.2 Dermatology Life Quality Index Questionnaire

The Dermatology Life Quality Index (DLQI) will be assessed at the visits specified in [Table 1](#). It is a simple 10-question validated questionnaire that has been used in more than 40 different skin conditions. Its use has been described in more than 1,000 publications, including many multinational studies. The DLQI is the most frequently used instrument in studies of randomized controlled trials in dermatology. The questionnaire is provided in [Appendix G](#).

## 7.3 Safety Assessments

### 7.3.1 Vital Signs

The following vital signs will be recorded at the visits specified in [Table 1](#) with the subject in a seated position, after having sat calmly for at least 5 minutes: systolic and diastolic blood pressure (mmHg), pulse (bpm), and body temperature (°C).

Weight (kg) and height (cm) will be collected to calculate the BMI and will be recorded at the visits specified in [Table 1](#). The height will only be recorded at the screening visit and the same value will be used for BMI calculation at other visits.

If deemed appropriate by the investigator, clinically significant findings in the vital signs will exclude a subject from study participation. Any abnormal finding related to vital signs that the investigator considers to be clinically significant must be recorded as an AE.

### 7.3.2 Physical Examination

The following sites/systems will at least be included in the physical examination, which will be performed at the visits specified in [Table 1](#):

- General appearance
- Dermatological (except atopic dermatitis)
- Head, eyes, ears, nose, throat (HEENT)
- Respiratory
- Cardiovascular
- Abdominal
- Neurological
- Musculoskeletal
- Lymphatic

Information for all physical examinations must be included in the source document. If deemed appropriate by the investigator, clinically significant findings in the physical examination will exclude a subject from study participation. Any significant change will be reported as an AE in the source document and eCRF.

### 7.3.3 Brief Physical Examination

The following sites/systems will at least be included in the brief physical examination that will be performed at the visits specified in [Table 1](#):

- General appearance
- Dermatological (except atopic dermatitis)
- Respiratory
- Cardiovascular
- Abdominal

Information for all physical examinations must be included in the source document. If deemed appropriate by the investigator, clinically significant findings in the physical examination will exclude a subject from study participation. Any significant change will be reported as an AE in the source document and eCRF.

### 7.3.4 Clinical Laboratory Tests

Laboratory tests will be performed at the visits specified in [Table 1](#). The tests will include urinalysis, hematology with differential, a standard chemistry panel (chemistry includes liver function tests and cholesterol), and serum pregnancy test (screening) for women of childbearing potential (WOCBP). At the visit specified in [Table 1](#), a urine pregnancy test will be performed for WOCBP (conducted at the investigator site). The specific tests in these panels are listed in [Table 5](#).

**Table 5: Clinical Laboratory Testing**

Laboratory Testing	Tests Included
Hematology	HCT, Hgb, MCH, MCHC, MCV, MPV, PLT, RBC, reticulocyte count, WBC, and differentials (neutrophils, lymphocytes, monocytes, eosinophils, and basophils relative and absolute)
Biochemistry	Albumin, alkaline phosphatase, ALT, AST, calcium, carbon dioxide, chloride, creatinine (enzymatic), CPK, GGT, glucose random, LDH, lipid panel (HDL, LDL, total cholesterol and triglycerides (non-fasting)), phosphorus, potassium, sodium, total bilirubin, TBIL (direct bilirubin reflex if elevated), urea (BUN), uric acid, CRP, total protein
Urinalysis	Color, clarity, pH, specific gravity, bilirubin, glucose, ketones, leukocytes, nitrite, blood, protein, urobilinogen and microscopic analysis (as required)
Urine pregnancy test	For females of childbearing potential (at each visit, except screening)
Laboratory tests required at screening only	
β-hCG for females of childbearing potential
 
FSH levels for women who have had a cessation of menses for at least 12 months without an alternative medical cause
 
Tuberculosis test (PPD or QuantiFERON-TB Gold)
 
Serology (HBV (HBsAg, anti-HBc), HCV, HIV)

ALT = alanine aminotransferase; anti-HBc = antibody to hepatitis B core antigen; AST = aspartate aminotransferase; β-hCG = β-human chorionic gonadotropin; BUN = blood urea nitrogen; CPK = Creatine phosphokinase; CRP = C-reactive protein; FSH = follicle-stimulating hormone; GGT = gamma-glutamyl-transferase; HBsAg = hepatitis B surface antigens; HBV = hepatitis B virus; HCT = hematocrit; HCV = hepatitis C virus; HDL = high-density lipoproteins; Hgb = hemoglobin; HIV = human immunodeficiency virus; LDH = lactate dehydrogenase; LDL = low-density lipoproteins; MCH = mean corpuscular hemoglobin; MCHC = mean corpuscular hemoglobin concentration; MCV = mean corpuscular volume; MPV = mean platelet volume; PLT = platelets; PPD = purified protein derivative; RBC = red blood cell (count); WBC = white blood cell (count).

Subjects who do not qualify to participate in the study due to a screening laboratory value abnormality can repeat the test once within the original screening time window, if the investigator believes there is a reasonable possibility that the subject would be eligible if re-tested.

If deemed appropriate by the investigator, clinically significant findings in clinical laboratory testing will exclude a subject from study participation. Any significant change will be reported as an AE.

### 7.3.5 Electrocardiogram

Twelve-lead ECGs will be performed as a safety assessment at the visits specified in [Table 1](#). Clinically significant findings in the ECG should exclude a subject from study participation (as deemed appropriate by the investigator). Any significant change will be reported as an AE.

## 7.4 Pharmacokinetic and Pharmacodynamic Assessments

### 7.4.1 Pharmacokinetics Assessments

Blood samples will be collected for PK assessment on visits and time points indicated in the schedule of events in [Table 1](#). Measurement of plasma concentrations of ASN002 will be performed in all subjects receiving ASN002 treatment. A few samples from each of the placebo subjects (e.g., pre-dose on Day 1 and 2 hours at Week 4) may be analyzed for quality control purposes.

The actual date and time of each blood sample collection will be recorded. Approximately 4 mL of blood will be collected for each time point.

Details about the collection, processing, handling, storage and shipping of blood samples will be provided in the laboratory manual.

Non-compartmental PK analysis will not be performed for this study.

Population PK analysis will be performed using nonlinear mixed-effects modeling approach with first-order conditional methods. This analysis may be combined with PK concentrations from other clinical trials in healthy and AD subjects as appropriate. The results from this analysis may be reported separately.

### 7.4.2 Pharmacodynamics Assessments

At selected study centers, for a subset of approximately 68 subjects who consent to the procedure, blood samples will be collected for PD analysis on visits indicated in the schedule of events in [Table 1](#). PD samples will be drawn as trough samples prior to the study product administration. PD samples will be obtained from the same subjects who consent to biopsy collection.

The actual date and time of each blood sample collection will be recorded. Approximately 8 mL of blood will be collected for each time point.

Details about the collection, processing, handling, storage and shipping of blood samples will be provided in the laboratory manual.

### 7.4.3 PK/PD Relationship Assessments

PK-efficacy, PK-safety and PK-biomarkers relationships will be explored using linear regression, loess plots, Hills functions, or logistic regression, as appropriate. The results from these analyses may be reported separately.

#### 7.4.4 Skin Biopsies

At selected study centers, for a subset of approximately 68 subjects who consent to the procedure, three or four optional skin biopsies will be collected at the visits specified in [Table 1](#). Two 4.5-mm punch biopsies (one from lesional skin and one from adjacent nonlesional skin) will be collected at Day 1, and one 4.5-mm punch biopsy will be collected from the same lesional skin (outside the scar of the previous biopsy, at least 1 cm away from the previous scar) at Week 12 or ET visit (if applicable). In addition, one 4.5-mm punch biopsy will be collected from the same lesional skin (outside the scar of the previous biopsy, at least 1 cm away from the previous scar) at Week 4 in subjects who consent to four skin biopsies. Biopsy samples will be obtained from the same subjects who consent to PD samples.

The skin will be cleaned, disinfected, and anesthetized before skin biopsies are performed. Sterile gauze will be used to absorb any bleeding. The biopsy sites will be sutured if necessary.

Each biopsy will be split in half. One part will be used for a limited immunohistochemistry panel and the other part will be used for gene expression analysis.

Details about the collection, processing, handling, storage and shipping of biopsy samples will be provided in the laboratory manual.

### 7.5 Other Assessments

#### 7.5.1 Medical Photography

At selected study centers, for a subset of approximately 68 subjects who consent to the procedure, medical photographs will be performed at the visits specified in [Table 1](#). Photographs of the area of worst eczema involvement will be taken to illustrate any visible clinical change. A target area for each participant will be identified at Day 1, and the same area will be photographed at the other visits. Care will be taken to use the same camera, the same magnification, and the same settings for each photograph at each visit in order to obtain comparable pictures. Medical photographs will be taken using a blue background.

Photographs will be identified and stored as instructed in the photography manual.

## 7.6 Adverse Events and Serious Adverse Events

### 7.6.1 Definition of Adverse Event

An AE is any untoward medical occurrence in a subject administered a pharmaceutical product and that does not necessarily have a causal relationship with this treatment. An AE can therefore be any unfavorable and unintended sign (including an abnormal laboratory finding), symptom, or disease temporally associated with the use of a study product, whether or not considered related to the study product. AEs and SAEs will be collected from the time of informed consent signature until the final visit / contact.

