## 1.2 Study Diagram

**Figure 1: Study Diagram**

\*The follow-up assessments at Week 16 will be for subjects who completed the study and declined to participate in the OLE study.

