 Brief physical examinations.

 Only at ET

 ECG will be recorded at 0 (pre-dose, within 1 hour of dosing), 1 (± 30 min), and 3 (± 1 hour) hours post-dose on Day 1 and Week 4. ECG will be recorded only once at screening, Week 12, and ET visits.

 If PPD is used, a second screening visit will be necessary.

 Optional, only for a subset of approximately 68 subjects who consent: two 4.5-mm skin biopsies at Day 1 (one from lesional skin and one from adjacent nonlesional skin) and one at Week 12/ET (from lesional skin). Subjects consenting to biopsies collection must also consent to PD samples. Biopsies should be collected prior to study product administration.

 Optional, only for a subset of approximately 68 subjects who consent: PD samples to be drawn as trough samples prior to study product administration. Subjects consenting to PD samples must also consent to biopsies collection. PD samples should be collected prior to study product administration.

 An additional skin biopsy from lesional skin and PD sample will be collected at Week 4 for subjects who consent to four biopsies.

 PK samples will be collected at 0 (pre-dose), 1 (± 30 min), 3 (± 30 min), and 6 (between 5 to 12 hours post-dose) hours post-dose. The dosing time for the previous day should be recorded accurately.

 PK samples will be collected at 0 (pre-dose) and 2 (± 30 min) hours post-dose. The dosing time for the previous day should be recorded accurately. At ET and Week 12, only one PK sample will be collected.

 Follow-up visit for subjects not participating in the OLE study. Subjects who have their study product discontinued due to the start of a prohibited medication for the treatment of AD or for any other safety reasons will be asked to come back for an additional follow-up visit about 4 weeks after the study product discontinuation (in addition to the ET visit). Refer to section 6.4.2 for more details.

 Study products will be taken at home daily for 12 weeks, except on study visit days when the study products will be administered on site. No drug administration will be given at Week 12 visit as part of the present study.

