#### 2.1.2 ASN002 in Atopic Dermatitis

ASN002 is an orally bioavailable, potent dual inhibitor of JAK and SYK kinases with 50% inhibitory concentrations (IC50 values) of 5-46 nM in biochemical assays. In cell-based mechanistic assays, the compound showed inhibition of IgE-immune complex induced degranulation and phosphorylation of LAT (Linker for Activation of T cells) a substrate of SYK, and also IL-6 induced phosphorylation of STAT3 (IC50 range 14–143 nM). In a collagen-induced arthritis model, ASN002 demonstrated a significant reduction in arthritic, histopathology and radiographic scores when compared to vehicle. The compound also showed broad antiproliferative activity in a panel of cell lines representing both solid and leukemia/lymphoma tumor types. The data from both in vitro (cell line) and in vivo efficacy

studies with ASN002 provide strong rationale for its evaluation in subjects with atopic dermatitis. In a Phase 1b study (ASN002AD-101), plasma concentrations of ASN002 were measured in subjects with atopic dermatitis following single and repeated once daily oral administration at 20, 40 and 80 mg. At steady state,  $C_{max}$  and AUC were dose dependent with approximately 1.5-fold or less accumulation compared to those on Day 1, and the mean elimination  $t_{1/2}$  were 7.3-13.7 hours. At 80 mg, the mean  $C_{max}$  and AUCtau of ASN002 at steady state were 252 ng/ml and 3340 ng\*hr/ml, respectively. The safety and tolerability profile of ASN002 at all dose levels was excellent. The most common adverse event (AE) observed was transient, mild headache, mostly restricted to Day 1 likely due to fasting. There were no clinically significant laboratory changes including hematological parameters observed in this study. ASN002 showed robust clinical efficacy with nearly all patients obtaining a 50% improvement in disease severity (EASI50) at 40 mg and 80 mg once daily and substantial decreases in patient-reported itch measured by Numeric Rating Scale (NRS) after 4 weeks of treatment.

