	

• Number of drug-related TEAEs

• Proportion of subjects withdrawing from worsening AD at Weeks 2, 4, 8, and 12

• Changes in vital signs, physical examinations, ECG, and safety laboratory tests

To evaluate the PK profile of ASN002 in subjects with moderate to severe AD	
Secondary pharmacokinetic endpoint:
 

• Measurement of plasma concentrations of ASN002 in all subjects receiving ASN002 treatment

Exploratory	
To assess population PK of ASN002 in AD subjects via a population PK analysis approach	

• Characterization of population PK parameters via nonlinear mixed-effects modeling

To evaluate PD and biomarkers for evidence of drug activity in subjects with moderate to severe AD	

• Change from baseline in expression levels and kinase activity of key disease pathways in skin biopsies, such as Th2 and other T helper cell axes

• Changes from baseline in cellular infiltrates of T-cells and dendritic cells

• Changes from baseline in epidermal hyperplasia measures (epidermal thickness, ki67, and K16 expression)

• Changes from baseline in mRNA and protein expression of differentiation markers

• Changes in inflammatory measures in peripheral blood using proteomics

To explore the relationships between PK exposure and clinical measurement (e.g., biomarker, efficacy, and safety) as appropriate	

• Changes from baseline in clinical safety, efficacy and biomarker measurements in relationship to PK exposure

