## 4 STUDY DESIGN

### 4.1 Overall Design

This study will be performed at approximately 50 study centers located in the United States, Canada and Germany.

This study is a randomized, double-blind, placebo-controlled, multicenter, Phase 2b study. Approximately 220 subjects with moderate to severe AD (as defined by a BSA involved with AD of  $\geq 10\%$ , an EASI  $\geq 16$ , and an IGA  $\geq 3$  at Day 1) will be included in this study to complete the study with at least 160 evaluable subjects. Subjects will be men or women, aged 18 to 75 years, inclusive, at the time of consent.

Each subject should read and sign an informed consent form prior to any screening procedures being performed. Subjects who fulfill all of the inclusion criteria and none of the exclusion criteria will be accepted into the study. After a screening period of no more than 30 days (from Day -30 to Day -1), eligible subjects will be randomized (1:1:1:1) on Day 1 to receive ASN002 at 40 mg, 60 mg, or 80 mg, or placebo once daily for 12 weeks. The treatment period will be followed by a 4-week follow-up period for subjects not participating in the open label extension (OLE) study. For scheduled study visits, subjects will come to the study centers on seven occasions: screening, Day 1, Weeks 2, 4, 8, and 12, and Week 16/ ET for subjects not participating in the OLE study.

Efficacy will be assessed by IGA, EASI, SCORAD, BSA, pruritus NRS (daily), and 5-D pruritus scale. Quality of life will be evaluated using POEM and DLQI.

Safety will be assessed by AEs, physical examination, vital signs, 12-lead ECG, and clinical laboratory tests.

Pre- and post-dose PK blood samples will be collected from all subjects on a sparse sampling schedule at Day 1, and Weeks 2, 4, 8 and 12 (or ET visit, if applicable).

At selected study centers, in a subset of approximately 68 subjects who consent, PD blood samples will be collected pre-dose on Day 1 and Week 12 (or ET visit, if applicable). PD samples will be obtained from the same subjects who consent to biopsy collection. An additional PD blood sample will be collected at Week 4 in subjects who also consent to four skin biopsies.

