### 7.6.2 Definition of Treatment-Emergent Adverse Event

A TEAE is any condition that was not present prior to treatment with the study product but appeared following treatment, was present at treatment initiation but worsened during treatment, or was present at treatment initiation but resolved and then reappeared while the individual was on treatment (regardless of the intensity of the AE when the treatment was initiated).

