13.1 Adverse Events

Adverse events (AEs) will be coded according to the Medical Dictionary for Regulatory Activities (MedDRA), Version 21.0.

Treatment emergent adverse event (TEAE) is any condition that was not present prior to treatment with the study product but appeared following treatment, was present at treatment initiation but worsened during treatment, or was present at treatment initiation but resolved and then reappeared while the individual was on treatment (regardless of the intensity of the AE when the treatment was initiated). See Appendix 2 for handling of completely or partially missing dates for AEs. In the case where it is not possible to define an AE as treatment emergent or not, the AE will be classified as treatment emergent.

	STATISTICAL ANALYSIS PLAN, Version Final 2.0
Protocol Number: ASN002AD-201 V3.0	Sponsor: Asana BioSciences, LLC

An overall summary table of adverse events will be provided. The number of events and the number and percentage of subjects who experienced AE, TEAE, TEAE by greatest reported relationship, TEAE by relationship, TEAE by highest reported severity, TEAE by severity, related TEAE by highest reported severity, related TEAE by severity, serious AE, serious TEAE, serious TEAE by greatest relationship, TEAE and related TEAE leading to study drug discontinuation, TEAE and related TEAE leading to study discontinuation, TEAE and related TEAE leading to treatment interruption and AE leading to death will be presented as well as TEAE of clinical relevance and of clinical interest.

TEAE of clinical relevance are:

- Neutropenia
- Lymphopenia
- Eosinopenia
- CPK elevation
- Headache
- Nausea
- Nasopharyngitis
- Diarrhea
- Vomiting

TEAE of clinical interest are:

- Thrombosis (deep venous thrombosis, pulmonary embolism, and arterial thrombosis)
- Anemia
- Arthralgia

Unless otherwise specified, a subject experiencing the same TEAE multiple times will be counted only once for the corresponding PT. Similarly, if a subject experiences multiple TEAEs within the same SOC, the subject will be counted only once for that SOC. TEAEs will be sorted alphabetically by SOC and within each SOC the PT will be presented by decreasing order.

Frequency and percentage of subjects who experience TEAE will be summarized by SOC and PT within SOC.

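### Adverse-event follow-up after the last dose depends on each subject's route out of the study, and the SAP plans no person-time rate or on-treatment TEAE summary to allow for it

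*Protocol*

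**What the plan says.** **Collection window.** Protocol section 7.6.1: "AEs and SAEs will be collected from the time of informed consent signature until the final visit / contact". No fixed number of days after the last dose is set, so the window closes wherever the subject's own last visit falls:

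- OLE entrants finish at Week 12. Table 1, footnote 13 gives no dose at that visit, so observation ends about 1 day after the last dose.
- Completers who decline the OLE go to Week 16. Section 4.1: "The treatment period will be followed by a 4-week follow-up period for subjects not participating in the open label extension (OLE) study". The note to Figure 1 is narrower: "The follow-up assessments at Week 16 will be for subjects who completed the study and declined to participate in the OLE study".
- Subjects stopped for a safety reason or for most prohibited AD medication have an early-termination (ET) visit and another about 4 weeks after stopping (section 5.3.1; Table 1, footnote 12; section 6.4.2, items 2 and 5).
- Subjects given oral corticosteroids for AD after Week 4 stop product but attend until Week 12 (section 6.4.2, item 4).
- Other drop-outs are asked for an ET visit, if they agree (section 5.3.1). Its timing relative to the last dose is not stated.

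**What counts.** Protocol section 7.6.2: "A TEAE is any condition that was not present prior to treatment with the study product but appeared following treatment". This new-onset limb has no end. The worsening and recurrence limbs are tied to the time on treatment. SAP section 13.1 repeats the definition and adds: "In the case where it is not possible to define an AE as treatment emergent or not, the AE will be classified as treatment emergent".

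**How it is reported.** Protocol section 3 lists the number of TEAEs and "Number of drug-related TEAEs" as safety endpoints. SAP section 13.1 reports numbers of events and numbers and percentages of subjects. SAP Appendix 1 makes subjects per arm the default denominator.

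**The concern.** Route is settled after randomisation and depends on response and tolerability. AD rescue in the first 4 weeks, for example, bars OLE entry (Protocol section 6.4.2, item 2). The sample-size section assumes an EASI change of at least -15 on active and -8 on placebo, so different rescue use and OLE uptake by arm would be no surprise.

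A subject followed for longer contributes more events at the same underlying rate. If the mix of routes differs by arm, the crude comparison of each dose with placebo can show a difference, or hide one, without any drug effect. Much of the extra time is also off drug: Protocol section 2.1.2 gives a mean half-life of 7.3 to 13.7 hours, so five half-lives are 36.5 to 68.5 hours, or 1.5 to 2.9 days, against a follow-up of 4 weeks.

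**Working it through.** **Inputs from the documents.** Treatment 12 weeks, follow-up 4 weeks, 55 subjects per arm, about 15% drop-out. The plan's own figures reproduce: 4 + 12 + 4 = 20 weeks maximum duration, and 46 / 0.85 = 54.1, rounded up to 55. The documents give no expected TEAE count to reproduce.

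**Assumptions.** OLE uptake u by arm, the weekly event rate r (equal in both arms), the time of drop-out, and the share of drop-outs who have the 4-week visit. None is in the documents.

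**Step 1: OLE uptake alone, all subjects complete.** Mean weeks observed W = 12 + 4(1 - u). Expected TEAEs = 55 x r x W, so the ratio between arms is the ratio of W.

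| u active | u placebo | W active | W placebo | Placebo / active |
|---|---|---|---|---|
| 80% | 80% | 12.8 | 12.8 | 1.000 |
| 90% | 70% | 12.4 | 13.2 | 1.065 |
| 80% | 50% | 12.8 | 14.0 | 1.094 |
| 90% | 60% | 12.4 | 13.6 | 1.097 |
| 60% | 90% | 13.6 | 12.4 | 0.912 |
| 100% | 0% | 12.0 | 16.0 | 1.333 |

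At r = 0.10 per week, 90% against 60% gives 55 x 0.10 x 12.4 = 68.2 and 55 x 0.10 x 13.6 = 74.8 TEAEs. The share of subjects with at least one TEAE, 1 - [u exp(-12r) + (1 - u) exp(-16r)], is 70.9% and 73.9%.

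**Step 2: off-drug rate half the on-drug rate.** The 4 weeks then count as 2. For 90% against 60%: (12 + 2 x 0.4) / (12 + 2 x 0.1) = 12.8 / 12.2 = 1.049. For 90% against 70%: 12.6 / 12.2 = 1.033. Extreme: 14 / 12 = 1.167.

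**Step 3: reasons for stopping.** Let 15% in each arm stop at a mean of Week 6, with share s having the 4-week visit: W = 0.85[12 + 4(1 - u)] + 0.15(6 + 4s). Time on treatment is equal in both arms, so only follow-up differs.

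- Uptake 80% in both, s = 20% active and 80% placebo: 10.88 + 1.02 = 11.90 against 10.88 + 1.38 = 12.26, ratio 1.03.
- Uptake 90% against 60%, same s: 10.54 + 1.02 = 11.56 against 11.56 + 1.38 = 12.94, ratio 1.12.

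**Step 4: what adjustment does.** With a constant rate, dividing by W returns r in both arms, ratio 1.00. If the off-drug rate is halved (90% against 60%), the rate over all follow-up is 12.2 / 12.4 = 0.984r on active and 12.8 / 13.6 = 0.941r on placebo, ratio 0.957. An on-treatment rate restores 1.00. Each summary therefore covers a gap that the other leaves.

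**The case against.** **Safety is descriptive.** Protocol section 8.3.3 rules out inferential statistics on safety. This stands: no test, alpha or primary conclusion is affected. Tables by dose against placebo are still read comparatively.

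**The plan gives the reader some help.** SAP section 13.1 also plans time to onset, duration and onset before or after 4 weeks for the most frequent TEAEs. SAP section 7.1 summarises days in study and numbers entering the OLE, SAP section 11 summarises days treated, and Protocol section 8.3.3 shows AE onset relative to dosing. An attentive reader could notice an imbalance. None of these links event counts to time observed, so the size would have to be guessed.

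**Counting inclusively is conservative.** This is a fair reason to keep the all-follow-up tables. A reader might infer that the named endpoint should instead be cut at five half-lives. The documents do not support that. An interval of 1.5 to 2.9 days is longer than the roughly 1 day for which OLE entrants are followed. The protocol itself uses 4 weeks after the last dose for contraception, and 4 weeks or 5 half-lives, whichever is longer, for live vaccines. A short cut-off would also move late events of clinical interest, such as thrombosis, out of the endpoint.

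**Drug-related TEAEs are probably less exposed.** Investigators judge relatedness blinded unless the code is broken, and temporal relationship is named evidence (Protocol section 7.6.4.1). Late off-drug events are less likely to be called related. This stands.

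**The wording about follow-up is looser elsewhere.** Table 1, footnote 12 begins "Follow-up visit for subjects not participating in the OLE study", which could be read to give every drop-out a Week 16 visit. The Figure 1 note limits the Week 16 assessments to completers who declined the OLE.

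**Conclusion.** The point holds as a reporting weakness of modest, unknown size. Unequal follow-up is written into the protocol, new-onset TEAEs have no upper limit, and nothing planned relates event counts to time observed. Under assumed uptake differences of 20 to 30 points, follow-up alone distorts the count ratio by about 5 to 12%: near 5% if the off-drug rate is half the on-drug rate, near 12% if reasons for stopping also differ. The mildest scenarios give about 3%. Balanced routes give none, and the ceiling is 33% if every subject completes. All of this rests on assumed uptake and stopping patterns, and either arm could be favoured.

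Two stronger readings go too far:

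- A reader might infer a distortion above 20%. Suppose 25% of placebo subjects stop at Week 5 with ET only and 10% of completers decline the OLE, against 10% stopping at Week 5 for safety and 30% declining on active. Weeks observed are 0.75 x 12.4 + 0.25 x 5 = 10.55 and 0.90 x 13.2 + 0.10 x 9 = 12.78, ratio 1.21. But weeks on treatment alone are 0.75 x 12 + 0.25 x 5 = 10.25 and 0.90 x 12 + 0.10 x 5 = 11.30, ratio 1.10, so about half is ordinary differential drop-out. The scenario also denies every placebo drop-out the 4-week visit that AD-rescue stops receive. With it, placebo has 0.75 x 12.4 + 0.25 x 9 = 11.55 weeks and the ratio falls to 1.11.
- A reader might infer that no part of the TEAE definition ends. Only the new-onset limb is open.

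**What to change.** In SAP section 13.1, keep the planned all-follow-up TEAE tables and add, per arm:

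1. TEAE rates per person-time of actual observation, beside the crude figures.
2. An on-treatment TEAE summary with the same cut-off for every subject. Either set it no later than the follow-up that every route provides (about 1 day after the last dose), or censor at each subject's end of observation and use person-time as the denominator. Show later-onset events separately as post-treatment.

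Both are needed. A last-dose cut-off alone does not equalise time on treatment, and a rate over all follow-up mixes on-drug with off-drug time.

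The cost is SAP wording and a few extra tables from dates already collected. The downside is that the tables must be read together. AE collection and SAE reporting do not change. Separately, Protocol section 7.6.7 can end SAE reporting when an alternative therapy begins, whereas section 7.6.1 collects SAEs to the final visit; those two passages must be reconciled.
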